**Principal Investigator**

On a quarterly basis, the PI will be the Study Monitor and will meet periodically with the Research Co-investigator(s) and research staff to discuss the current findings and analysis. During these meetings, the PI will also be responsible for verifying data accuracy, and compliance with the study protocol.

**Research Coordinator**

As the coordinator, he will be responsible for providing data management support to the PI by collecting and documenting the required study data. This information will be documented in a secure, excel spreadsheet with appropriate subsections to distinguish the various types of data/events. Each quarter, the Research Coordinator will meet with the PI and Co-Investigator(s) to discuss the current findings/analysis, concerns/issues (unanticipated problems and adverse events), and the overall study in general.

**III. Timeframes for reporting adverse events and unanticipated problems to the monitoring entity**

All reportable events will be sent to the IRB in accordance with the timeframes specified by NYU School of Medicine guidelines. The Principal Investigator will have the responsibility of completing and submitting a Reportable Events form to the IRB. This form can be found at the following web address:

<http://irb.med.nyu.edu/for-researchers/other-submissions-and-reviews/events-and-information-require-prompt-reporting-irb-re>

**IV. Frequency of monitoring entity's assessment of data or events**

The study monitor will assess all safety data immediately as they occur. Study data will be assessed on a weekly basis.

**V. Specific triggers or stopping rules**

In case UADEs or SAEs occur, which are thought to be possibly related to steroid or Platelet-Rich-Plasma injections and are considered to be a potential health risk for participating subjects, the study monitor who is also de PI will report this information immediately to the IRB. At this point, the PI may decide, in consultation with the participating Investigators, to either 1) postpone treatment of newly-enrolled patients and to discontinue the treatment of established study subjects or 2) close out the study. If the study is postponed, the study will not resume until the investigators have thoroughly examined the event(s) and conclude that continuation of the clinical trial is justified. A review of the event, by the IRB, the PI, or both, may necessitate modifications to the protocol to ensure patient safety.

**VI. Procedures for communicating the outcome of the reviews by the Monitoring Entity to the IRB, the study sponsor, and other appropriate entities**

Outcomes of monitoring reviews will be communicated to the IRB through quarterly summaries/reports that will include a narrative on all adverse and reportable events (previously reported or not, serious or not), as well as any proposed changes to the protocol and/or study analysis.

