Platelets-Rich-Plasma group: Patients will be asked to stop taking any type of anti-inflammatory medication from 7 days before the procedure to 2 weeks after. At the moment of the procedure, at CMC, the radiology team will draw 30cc of venous blood from the patient and the blood will be processed with the PRP kit and centrifuged in the SmartPrep PRP machine.. The patient is then scanned prone using a linear 14 or 9 MHz transducer. A 20 Gauge spinal needle is usually employed for purposes of aspiration. We can use sterile saline to confirm needle placement in the cyst in lieu of lidocaine and then inject the PRP by the radiologist.

The procedure will be done without using any local anesthetic to avoid pharmacological interaction with the injected substance. A compression bandage will be placed locally for 7 days. Investigators will monitor any side effect from the injection and treat the patients per standard care, this can include

prescription of analgesics. No remaining biomaterial or any blood sample will be collected or stored for future studies.

It must be noted that the radiology team (technicians and radiologist) in charge of the PRP processing and handling, are well trained in this matter, since they have been using PRP and Harvesttech SmartPrep PRP machine in a weekly and sometimes daily basis, as part of patient's treatment or as part of previous clinical trials. [name], who is one of the Co-investigators, will be the radiologist supervising the study in the radiology department, to minimize any potential risk, and assuring appropriate preparation of the product and execution of the procedure.

**Corticosteroid group:** Patients will be asked to stop taking any kind of anti-inflammatory medication from 7 days before the procedure to 2 weeks after.. The radiology team will draw 30cc of blood from the patient, and this blood will then immediately be discarded out of sight from the patient. The blood does not need to be used for the control group, and none of it will be stored for future use. Blood draw is crucial in this group as it will keep the research activities consistent between the groups and prevent any patient from knowing if they are in the treatment or control group. It is crucial to keep the patient blinded for the study to eliminate any bias in the outcomes.

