The Principal Investigator for this study will also serve as the Study Monitor. He will conduct interim monitoring of accumulated data from research activities to assure the continuing safety of research participants, relevance of the study hypothesis, appropriateness of the study, and integrity of the accumulating data.

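### After a postponement for a possibly related serious event, the only stated restart condition is the investigators' own conclusion; IRB agreement should be added (minor, cheap improvement)

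*Combined protocol and SAP*

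**What the plan says.** The rule is in Section 4.III (Data Safety Monitoring Plan), part V. Its trigger has two parts, and both must be met: an SAE or UADE is thought possibly related to the steroid or PRP injection, and it is considered a potential health risk to participants. The PI then reports to the IRB immediately. After that, "the PI may decide, in consultation with the participating Investigators", whether to postpone treatment or to close the trial.

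For a postponement, the plan says that "the study will not resume until the investigators have thoroughly examined the event(s) and conclude that continuation of the clinical trial is justified". It continues: "A review of the event, by the IRB, the PI, or both, may necessitate modifications to the protocol to ensure patient safety".

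Other sections fix who holds which role:

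- Section 4.III, part I.a: the PI classifies the relationship of each adverse event to treatment.
- Section 4.III, part II: "The Principal Investigator for this study will also serve as the Study Monitor". In that capacity the PI "will meet periodically with the Research Co-investigator(s) and research staff to discuss the current findings and analysis".
- Section 4.I, PRP group: the radiologist "who is one of the Co-investigators, will be the radiologist supervising the study in the radiology department", with the aims of keeping risk low and of "assuring appropriate preparation of the product and execution of the procedure".
- Section 4.III, parts III and VI: reportable events go to the IRB within the institution's timeframes, and the outcomes of monitoring reviews go to it in quarterly reports.

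**The concern.** A postponement under this rule follows a serious event that the trial team itself thinks may have been caused by the injection. Whether to expose further patients is then the most consequential safety decision in the trial. As written, the same small group judges relatedness, monitors the data, decides on the pause and reaches the conclusion that lifts it. A co-investigator who oversees the product and the procedure is not excluded from that conclusion. Section 5.I says there are no data on PRP in a Baker's cyst, so experience with this use offers little reassurance. An outside body already receives the immediate report, yet the restart sentence gives it no stated part.

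**Working it through.** The plan gives no figure for this point, so the main check is of the text. The arithmetic only shows how many patients the rule could cover.

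**Step 1. Look for IRB agreement as a restart condition.**

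- Restart sentence (4.III, part V): it names the investigators' examination and conclusion, and does not mention the IRB.
- Review sentence (same part): review may be by the IRB, by the PI, or by both. A review by the PI alone meets this wording. The stated consequence is a possible protocol change, not permission to restart.
- Immediate report (same part): this is notification, with no requirement to wait for a reply.
- Parts III and VI: these set reporting timeframes and quarterly reports. On this text, the outcome of the investigators' review could reach the IRB in a quarterly report after injections had resumed.

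No section makes IRB agreement a condition of restart.

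**Step 2. Patients still to be injected when restart is decided.** Inputs from Section 3.I and Section 4.I: 50 patients, 25 per arm, one injection each. Assumption: the trigger is equally likely to follow any of the 50 injections. If it follows injection k and treatment stops before the next one, 50 − k patients remain.

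- Mean of (50 − k) over k = 1 to 50: (50 × 49 / 2) / 50 = 1225 / 50 = 24.5, with a range of 0 to 49.
- PRP share under equal allocation: 24.5 / 2 = 12.25.

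This average is a ceiling. If d more injections are given before the event appears, is recognised and leads to a pause, the mean becomes (50 − d)(49 − d) / (2 × 50):

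- d = 0: 50 × 49 / 100 = 24.5
- d = 5: 45 × 44 / 100 = 19.8
- d = 10: 40 × 39 / 100 = 15.6

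The values of d are illustrative. Section 3.I also counts screen failures within the 50, so fewer patients may be injected, which lowers the figure further.

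**Step 3. How often the rule might be used.** The documents give no rate of related serious events. With an assumed 0.1% to 0.5% per patient:

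- 1 − 0.999^50 = 4.9%
- 1 − 0.995^50 = 22.2%

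These count any related SAE. The actual trigger is narrower, because the event must also be considered a potential health risk. The one numerical event rate in Section 5.I is PRP local infection below 1%. It bounds the chance of any infection in 25 PRP patients at 1 − 0.99^25 = 22.2%, and not all infections would be serious.

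Multiplying the two steps gives roughly 0.049 × 24.5 = 1.2 to 0.222 × 24.5 = 5.4 patients covered by the restart rule, before knowing whether a trigger occurs.

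**The case against.** **The restart sentence sets a minimum.** It says what must happen before the study resumes, not that this is enough. Institutional rules that we cannot see may also require IRB agreement. This stands as a limit: the documents cannot show that IRB agreement would be absent in practice. What they show is that the protocol does not state it, and that the only condition it does state can be met by the investigators alone.

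**The IRB is not bypassed.** A reader might infer that the plan shuts it out. The text does not support that. The IRB is told immediately, is named as a possible reviewer and receives quarterly reports on all events, and nothing limits its power to intervene.

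**The trigger is narrow.** A reader might also take every possibly related serious event to start this process. The second condition, potential health risk, rules that out. That second judgement is not assigned to anyone independent either, but it does make a pause less likely.

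**The radiologist's role is partly protective.** Section 4.I gives risk reduction as a reason for the supervision. The text does not say that this person would take part in the restart decision; it only does not exclude it. The point therefore rests on the missing IRB condition and does not depend on any one person's conflict.

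**Close-out.** Because part V also lets the PI "close out the study" without mentioning follow-up, a reader might infer that injected patients would lose their remaining visits. The documents do not support this. Section 4.I and both schedules of events set visits at 12 and 24 weeks, part I.a plans adverse-event documentation to the final study visit, and nothing cancels either. A sentence on this would only restate what is already scheduled.

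**Conclusion.** The point holds as a minor safety improvement: the stated condition for restarting injections is the investigators' own conclusion, and IRB agreement is not part of it. The conclusion rests on the protocol text alone and makes no claim about institutional rules outside it.

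The scale is modest. Given a trigger, at most about 24.5 patients on average (about 12 of them PRP) would still be uninjected, assuming equal likelihood after each of 50 injections and a pause before the next one. No harm to any of them is implied. The trigger itself is probably uncommon. The design figures in Section 3.I are not affected.

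**What to change.** Replace the restart sentence in Section 4.III, part V, with: *After any postponement, injections will restart only when the investigators have examined the event or events and the IRB has reviewed the report and agreed that the trial may continue.*

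This changes wording only. It needs no new committee, visit or procedure, because the IRB already receives the immediate report. The downside is that a pause may last longer while the IRB replies. Some patients enrolled but not yet injected may then have to repeat the 7-day stop of anti-inflammatory medication required before the procedure (Section 4.I).

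The fix has one limit. Postponement is at the PI's discretion, so the new sentence has no effect if the PI decides not to pause.

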**IV. Data Storage and Confidentiality**

All research data will be recorded into a password-protected database and stored in the offices of the investigators on a password-protected computer. After initial data collection, all private health information will be removed, and patients will be tracked with an anonymous study number. The collected data will be permanently deleted immediately after the completed study is accepted in full for publication.

## 5. RISKS AND BENEFITS

### I. Risks:

Subjects involved in the study will be at risk of complications associated with the injection such as pain at the site of the injection, infection, bleeding or hematoma formation.

Subjects in the Corticosteroid group: Studies have shown that corticosteroid injection into soft tissues is safe, and no serious unexpected reactions have been reported. In general, corticosteroid injection into the cyst may result in local atrophy and post injection flare but the use of Triamcinolone lowers the frequency of these complications from happening due to its pharmacological characteristics.

Subjects in the PRP group: Although There has been no data about using PRP into a baker's cyst, studies have stated that the side effects of Platelets-Rich-Plasma injections in soft tissues are very limited as the patients are utilizing their own blood. The main risk includes local infection (less than 1%) and flare reaction beginning the day after the injection.

Breach of confidentiality is an unlikely, but possible risk to subjects included in this study.

### II. Protection Against Risks:

Medical protection for Corticosteroid group: Studies have reported that the use of triamcinolone acetonide and its dilution with lidocaine without epinephrine decrease the risk of local atrophy and post injection flares. Study investigators will monitor any side effect from the injection and treat them per standard practice. This can include prescription of oral anti-inflammatory medications or analgesics, provision of counseling for self-management by the patient and referral for further treatment as necessary.

Medical Protection for PRP group: The study investigators will monitor the patients and any side effect from the injection and treat them as necessary, including the prescription of analgesics, provision of counseling for self-management by the patient and referral of the patient for further treatment if needed.

All patients will be deidentified and given a code. Information linking the patient codes to the participants' names and medical record numbers will be stored in a secure location separate from the medical information. Access to the information linking the linkage codes with participant identifiers shall be documented.

Participant medical information will be stored electronically within a password protected spreadsheet available only to the PI, co-investigators, and research staff as necessary for data analysis. The names and medical record numbers of the study participants will be deleted from their stored medical information and replaced with a linkage code. Access to participant medical information contained within the registry will be restricted.

### III. Potential Benefits to the Subjects:

The main benefit to patients will be future adjustments to recommend Ultrasound-guided Platelets-Rich-Plasma injection versus Ultrasound guided Corticosteroid Injection for management of symptomatic baker's cyst.

#### IV. Costs/Reimbursement

All study-related costs associated with the subject being in this study will be paid by the sports division of the orthopedic department. The patient or the insurance of the patient, will be charged or held responsible for the costs of the routine care of the baker's cyst. (The care would be received by the patient if were not participating in the study)

The Patient will not receive any compensation for participating in this study.

#### 6. SUBJECT IDENTIFICATION

##### Method of Subject Identification and Recruitment:

Subjects will be identified prospectively by investigator and co-investigator during office visit, and patients will be consented right after the office visit by one of our research personnel, the research personnel will be properly trained to describe in detail every item of the written consent form, and answer any question that the subjects may have. After being consented, the subjects will decide whether or not to participate in the study, if they decide to do so, They will sign and receive a copy of the written consent form. In order to minimize the risk of breach of confidentiality, we will maintain the data and informed consent forms on a secure and password protected database accessible only to study staff. After initial data collection, all private health information will be removed, and patients will be tracked with an anonymous study number. The collected data will be permanently deleted immediately after the completed study is accepted in full for publication.

